**No dose modification will be pursued for tamoxifen.**

**Hematologic Toxicity\***

**Adverse Event:\* Neutropenia**

While dose hold may apply for all days of occurrence, dose modification will only apply if neutropenia persists for day 1, 8, and 15 of each cycle. Dose modifications are not required if labs are drawn on other days and counts have recovered upon retreatment on days 1, 8, 15.

Neutropenia Febrile neutropenia	Management/Next Dose for Vorinostat
ANC $\geq$ 1000	100%
ANC: 500-1000	Hold for until $\leq$ grade 2 #, Restart at 75%: 300 mg qd for all subsequent cycles Second occurrence resume at 200 mg qd for all subsequent cycles Third occurrence: remove from study
ANC: 0-500	Hold for until $\leq$ grade 2 or less# Restart at 75%: 300 mg qd for all subsequent cycles Second occurrence resume at 200 mg qd for all subsequent cycles Third occurrence: discuss with sponsor and principal investigator, consider omitting alternate weeks

#Patient with a dose delay for more than 3 weeks in the first 2 cycles will need to be replaced for toxicity and efficacy assessments.

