#### **7.1.1 Definitions**

##### **Evaluable for toxicity**

All participants will be evaluable for toxicity from the time of their first treatment with pembrolizumab, vorinostat, and tamoxifen.

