## **7.2 Evaluation of Safety**

The safety parameters for this study include all laboratory tests and hematological abnormalities, physical findings, and spontaneous reports of adverse events reported to the investigator by participants.

Toxicity will be assessed according to the NCI CTCAE version 5.0. Safety analyses will be performed for all participants who have received at least one dose of study drug.

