### 8.1 Sample Size Considerations

#### 8.1.1 Sample Size and Power Estimate

For Arm A (pembro + vorinostat + TAM): The null hypothesis that the true response rate for pembrolizumab and vorinostat in ER+ pretreated patients alone without biomarker enrichment is 0.15 which will be tested against the alternative that response rate of pembrolizumab in a biomarker select population is 0.40. In the first stage, 13 patients will be accrued. If there are 2 or fewer responses in these 13 patients, the study will be stopped. Otherwise, 22 additional patients will be accrued for a total of 35. The null hypothesis will be rejected if 10 or more responses are observed in 35 patients. This design yields a type I error rate of 0.025 and power of 0.9 in this treatment arm when the true response rate is 0.4 in this patient subpopulation.

For Arm B (pembro + TAM): The null hypothesis that the true response rate for pembrolizumab in ER+ pretreated patients alone is 0.10 which will be tested against the alternative that response rate of pembrolizumab in a biomarker select population is 0.35. In the first stage, 11 patients will be accrued. If there are 1 or fewer responses in these 11 patients, the study will be stopped. Otherwise, 19 additional patients will be accrued for a total of 30. The null hypothesis will be rejected if 7 or more responses are observed in 30 patients. This design yields a type I error rate of 0.025 and power of 0.9 in this treatment arm when the true response rate of pembro and TAM treatment is 0.35 in this patient subpopulation.

Based on earlier results in Section 1.3 and hypothesized treatment effects, we will most likely to enroll 46 evaluable patients (~65% chance), whereas the possible enrollment ranges from 24 to 65. For the comparison of the treatment arms, the proposed design will have 72.53% power for the Fisher's exact test at 0.1 significance level when the true response rates are 0.4 and 0.1 for the immune priming and the no immune priming treatment arm.

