## 8.3 Analyses Plans

### 8.3.1 Analysis Population

We will conduct an intention-to-treat analysis of efficacy. All randomized patients will be evaluated.

For evaluation of safety, we will restrict the arm-specific samples to all patients who have received at least one dose of investigational therapy.

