### 8.3.2 Primary Analysis (or Analysis of Primary Endpoints)

#### Primary Endpoint 1 Analysis (Evaluation of Efficacy)

For each arm objective response rate (ORR) will be defined as the proportion of participants randomized to that arm whose status is SD or better (CR, PR) at 24 weeks' follow-up. Within each treatment arm, the observed ORR will be compared to the respective null (ineffective) rate using the decision rule provided by the Simon's two-stage design. In addition to calculating the ORR, we will calculate the corresponding one-sided 95% confidence interval by appropriately accounting for the Simon's two-stage design: given the observed response number ( $s$ ), testing of the null hypothesis of  $H_0: p \leq p_0$  will reject the null if the probability of observing as many or less than the observed number of responses ( $s$ ) is less than the significance level:  $\text{Prob}(S \leq s | p_0) < \alpha$ . Using this hypothesis inversely, we can construct a  $(1-\alpha)100\%$  one-sided confidence interval is given as a set

$$\{p: \text{Prob}(S \leq s | p_0 = p) < \alpha\}$$

where  $\text{Prob}(S \leq s \mid p_0 = p)$  indicates the joint distribution of stage to stop and observed response number ( $s$ ) as in Chang et al., 1989. Similarly, the observed rates will be compared between the treatment arms using the Z-test and appropriately accounting for the Simon's two-stage design.

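### The replacement footnote under the vorinostat neutropenia table contradicts the intention-to-treat efficacy set and the at-least-one-dose safety set

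*Combined protocol and SAP*

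**What the plan says.** - **Section 5.2, neutropenia table.** The two rows that call for a hold carry a # mark. Its footnote says that a patient with a "dose delay for more than 3 weeks in the first 2 cycles will need to be replaced for toxicity and efficacy assessments". The dosing column is headed "Management/Next Dose for Vorinostat", and only Arm A receives vorinostat (Tables 5.2 and 5.3).
- **Section 8.3.1, efficacy.** "We will conduct an intention-to-treat analysis of efficacy. All randomized patients will be evaluated".
- **Section 8.3.2, primary endpoint.** The response rate in each arm is the "proportion of participants randomized to that arm whose status is SD or better" at 24 weeks.
- **Section 8.3.1, safety.** "we will restrict the arm-specific samples to all patients who have received at least one dose of investigational therapy". Section 7.2 agrees: "Safety analyses will be performed for all participants who have received at least one dose of study drug". So does Section 7.1.1: "All participants will be evaluable for toxicity from the time of their first treatment with pembrolizumab, vorinostat, and tamoxifen".
- **Section 8.1.1, Arm A.** Stage 1 has 13 patients, and the arm stops at 2 or fewer responses. At the end, "The null hypothesis will be rejected if 10 or more responses are observed in 35 patients". The stated type I error is 0.025 at a true rate of 0.15, and the stated power is 0.9 at 0.40.

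Section 8 makes no provision for replacing patients.

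**The concern.** The footnote is mandatory and names both toxicity and efficacy. Site staff who follow it and a statistician who follows Section 8.3 would build different datasets. The word replaced has two readings, and each causes a problem.

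1. **Dropped and substituted.** This removes patients after randomization because of a toxicity, in one of two randomized arms. Arm A's response rate is then no longer the intention-to-treat rate, and the comparison with Arm B is affected too. Patients with prolonged neutropenia delays also leave the safety summary. Their adverse events are still entered and reviewed under Section 7.3.6, so only the summary set is affected.
2. **Kept, with another patient added.** Arm A then exceeds the 13 and 35 patients on which its cut-offs rest, and no rule says which patients count. If the cut-offs stay where they are, the stated 0.025 no longer holds.

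Stage 1 turns on 2 versus 3 responses in 13, so whether one patient counts can decide whether Arm A continues.

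**Working it through.** **Do the sets conflict?** A delay in cycle 1 or 2 can occur only in a patient who has been randomized and has started treatment. That patient is in the efficacy set of Sections 8.3.1 and 8.3.2 and in the safety set of Sections 7.1.1, 7.2 and 8.3.1. The footnote has the same patient replaced for both purposes. The conflict needs no arithmetic.

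**Inputs for the size (Section 8.1.1).** n1 = 13, continue if more than 2 respond; n = 35, reject if 10 or more respond; null rate 0.15, alternative 0.40.

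**Formula.** P(reject) = Σ over x from 3 to n1 of P(X1 = x) · P(X2 ≥ 10 − x), with X1 ~ Bin(n1, p) and X2 ~ Bin(n − n1, p).

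**The plan's own figures.** With n1 = 13 and n − n1 = 22, the result is 0.0249 at p = 0.15 and 0.904 at p = 0.40. Both stated figures are reproduced. The chance of passing stage 1 at p = 0.15 is 0.308.

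The documents give no rate of such delays, and the pilot summaries in Sections 1.3.1.2 and 1.5 list no neutropenia. The numbers of patients below are therefore assumptions.

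**Kept and added, cut-offs unchanged at 2 and 10, p = 0.15**

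| Extra patients | n1 | n | Type I error | P(pass stage 1) |
|---|---|---|---|---|
| none | 13 | 35 | 0.0249 | 0.308 |
| 1 in stage 2 | 13 | 36 | 0.0294 | 0.308 |
| 2 in stage 2 | 13 | 37 | 0.0342 | 0.308 |
| 3 in stage 2 | 13 | 38 | 0.0395 | 0.308 |
| 5 in stage 2 | 13 | 40 | 0.0512 | 0.308 |
| 1 in stage 1 | 14 | 36 | 0.0310 | 0.352 |
| 2 in stage 1 | 15 | 37 | 0.0379 | 0.396 |

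**Dropped and substituted.** Let a fraction q of Arm A be replaced, and let those patients respond at k times the null rate. If the intention-to-treat rate is 0.15, the rate among retained patients is 0.15(1 − qk)/(1 − q). For example, q = 0.05 and k = 0 gives 0.15/0.95 = 0.158; q = 0.10 and k = 1.5 gives 0.15 × 0.85/0.90 = 0.142. Putting the retained rate into the 13/35 rule gives the chance of rejecting:

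| Response of replaced patients | q = 1% | q = 5% | q = 10% |
|---|---|---|---|
| none respond (k = 0) | 2.66% | 3.42% | 4.73% |
| half the null rate (k = 0.5) | 2.57% | 2.93% | 3.48% |
| equal (k = 1) | 2.49% | 2.49% | 2.49% |
| 1.5 times the null rate (k = 1.5) | 2.42% | 2.11% | 1.73% |

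The expected number replaced to reach 35 retained patients is 35q/(1 − q), that is 0.4, 1.8 and 3.9.

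**The case against.** The trigger is narrow: neutropenia severe enough for a hold, lasting more than 3 weeks, within the first two cycles. The pilot of the same combination lists no neutropenia. With 1% replaced, the type I error stays between 2.4% and 2.7%, and the larger cases have no support in the documents. The inflation from added patients also assumes that nobody adjusts the cut-offs. All of this stands, and it limits the size of the point.

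A statistician would probably follow Section 8.3 over a footnote to a dosing table. That is likely for the final analysis, but it does not settle whether substitutes are enrolled or who makes up the 13 and the 35.

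The footnote might refer only to the six-patient toxicity look in Section 8.2 and to the stage counts. That would ease the conflict over the safety set, but not the conflict with the decision rule in Section 8.3.2. Elsewhere the plan does not remove delayed patients automatically: Section 5.2 (hepatic dysfunction) and Section 6 ask for contact or discussion after long delays, and footnote 3 of the study calendar lets some patients stay on study. Those texts concern staying on study, not who is analysed.

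Finally, the restriction to Arm A is inferred from where the marks sit; the footnote itself names no drug or arm. If it was meant more widely, the conflict with Section 8.3 is wider too.

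**Conclusion.** The concern holds. As written, the footnote cannot be followed together with the analysis populations in Sections 7.1.1, 7.2, 8.3.1 and 8.3.2. The textual contradiction is certain. Its numerical effect cannot be derived from the documents and is probably small. In the illustrative cases above, Arm A's type I error runs from 2.9% to 5.1% if patients are kept and added with unchanged cut-offs, and from 1.7% to 4.7% if they are dropped, against the stated 2.5%. Under dropping, the direction of bias depends on how the replaced patients respond, which is unknown. The point should be corrected, because it concerns who counts in the primary decision rule and that should be fixed before the data are seen.

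**What to change.** 1. Delete the # footnote sentence and its two marks. Alternatively, reword it to say that such patients stay in the intention-to-treat and safety sets of Section 8.3.1 and are not substituted.
2. In Section 8.3.2, state that Arm A's decision counts use the first 13 and the first 35 patients randomized to that arm, including any patient with such a delay. This is one workable convention; what matters is that one is stated.
3. State that any analysis using replacement patients is supportive only.
4. Reconcile Section 5.2 with Sections 7.1.1, 7.2, 8.3.1 and 8.3.2. The response-evaluable definition in Section 7.1.1 and the reference to evaluable patients in Section 8.1.1 raise the same question and are best settled together.

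No hold, delay or dosing rule is proposed here.

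**Cost.** The change is wording only, made through an amendment with the approvals that Section 9.4 requires. The sample size, visits and data collection do not change. The 0.0249 and 0.904 hold for true intention-to-treat rates of 0.15 and 0.40. Compared with dropping these patients, Arm A's reported rate may be slightly lower if they respond less often than the rest, or slightly higher if they respond more often. If the 0.40 was meant only for patients without such a delay, and delayed patients never respond, the intention-to-treat rate is 0.40(1 − q). Power is then 0.864 at q = 5% (rate 0.38) and 0.812 at q = 10% (rate 0.36).

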**Adverse Event: Anemia**

Hemoglobin	Management/Next Dose for Vorinostat
>8 mg/dl	100 %: 400 mg qd
6.5-8 mg/dl	75 %: 300 mg qd
<6.5 mg/dl	50 %: 200 mg qd

An alternative to dose modification in cases of anemia only would be the use of PRBC transfusion.

**Adverse Event: Thrombocytopenia**

While dose hold may apply for all days of occurrence, dose modification will only apply if thrombocytopenia persists for day 1, 8, and 15 of each cycle. Dose modifications are not required if labs are drawn on other days and counts have recovered upon retreatment on days 1, 8, 15.

Platelets	Management/Next Dose for Vorinostat
>75'000	100 %: 400 mg qd
<75'000	100 %: 400 mg qd
$\leq$ 50'000/mm 	Hold until $\leq$ grade 2 or less Restart at 75%: 300 mg qd for all subsequent cycles Second occurrence resume at 200 mg qd for all subsequent cycles Third occurrence: discuss with sponsor and principal investigator, consider omitting alternate weeks
$\leq$ 25'000/mm 	Hold until $\leq$ grade 2 or less Restart at 75%: 300 mg qd for all subsequent cycles Second occurrence resume at 200 mg qd for all subsequent cycles Third occurrence: remove from study

An alternative to dose modification in cases of anemia only would be the use of PRBC transfusion.

**Adverse Event: Non-hematological toxicities**

Laboratory abnormalities must be clinically relevant, and dose and drug-related to prompt dose modifications, in case of uncertainty doses may be re-escalated if toxicities recover.

Bilirubin	Management/Next Dose for Vorinostat
≤1.5 mg/dl	100 %: 400 mg qd
1.6 – 3.0 mg/dl	75 %: 300 mg qd
> 3.0 mg/dl	First occurrence: hold until ≤grade 2, 75 %: 300 mg qd Second occurrence: Hold until grade 2 or less, 50 %: 200 mg qd
AST/ALT	Management/Next Dose for Vorinostat
≤2.5 x ULN	100 %: 400 mg qd
2.5-5 x ULN	First occurrence: 75 %: 300 mg qd Second occurrence: 50 %: 200 mg qd
> 5 x ULN	First occurrence: hold until ≤grade 2, resume at 75 %: 300 mg qd Second occurrence: Hold until grade 2 or less, 50 %: 200 mg qd Third occurrence: remove from study

**Hepatic Dysfunction:** Any new increase in LFTs should raise the concern to rule out progressive metastatic disease. If the rise is not due to progressive metastatic disease, give the following dose based on lab values obtained on day 1 of each cycle:

**Effects on the liver:** Tamoxifen has been associated with changes in liver enzyme levels, and on rare occasions, a spectrum of more severe liver abnormalities including fatty liver, cholestasis, hepatitis, and hepatic necrosis. A few of these serious cases included fatalities. In most reported cases, the relationship to tamoxifen was uncertain. However, some positive rechallenges and dechallenges have been reported. If grade 3 or 4 liver toxicity is maintained after a temporary stopping of vorinostat, both drugs should be stopped. Any rechallenge should be discussed with the study chair. **If treatment is delayed for more than 3 weeks, contact the Principal Investigator.**

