## 5.2 Dose Modifications and Dosing Delays

The following dose modification rules will be used with respect to potential toxicity. Toxicity will be assessed according to the NCI CTCAE version 5.0.

The following dose modifications should be made for febrile neutropenia, and blood counts obtained on day one of each cycle. If more than one of these conditions applies, use the most stringent (i.e., the greatest dose reduction). **The AE may be due to pembrolizumab or vorinostat alone in which case the respective agent should be reduced. If overlapping toxicity is suspected, both drugs may be reduced with the potential to re-escalate the non-offending agent. Given the very different nature of pembrolizumab and vorinostat/tamoxifen toxicities, separate tables are shown for individual agents.**

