#### **Attribution of Toxicity:**

When study interventions are administered in combination, attribution of an adverse event to a single component is likely to be difficult. Therefore, while the investigator may attribute a toxicity event to the combination, to Vorinostat or Tamoxifen alone, or to pembrolizumab alone, for adverse events listed in Table 5.4, both interventions must be held according to the criteria in Table 5.4 Dose Modification and Toxicity Management Guidelines for Immune-Related Adverse Events Associated with Pembrolizumab.

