#### **Holding Study Interventions:**

When study interventions are administered in combination, if the AE is considered immune-related, both interventions should be held according to recommended dose modifications.

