#### **Restarting Study Interventions:**

Participants may not have any dose modifications (no change in dose or schedule) of pembrolizumab in this study, as described in Table 5.4.

- If the toxicity does not resolve or the criteria for resuming treatment are not met, the participant must be discontinued from all study interventions.
- If the toxicities do resolve and conditions are aligned with what is defined in Table 5.4, the combination of Vorinostat, Tamoxifen and pembrolizumab may be restarted at the discretion of the investigator. In these cases where the toxicity is attributed to the combination or to Vorinostat or Tamoxifen alone, re-initiation of pembrolizumab as a monotherapy may be considered at the PI's discretion.

**Table 5.4 Dose modification and toxicity management guidelines for immune-related AEs associated with pembrolizumab monotherapy and IO Combinations**

irAEs	Toxicity Grade (CTCAE v5.0)	Action With Pembrolizumab	Corticosteroid and/or Other Therapies	Monitoring and Follow-up
Pneumonitis	Grade 2	Withhold	
 
• Administer corticosteroids (initial dose of 1 to 2 mg/kg prednisone or equivalent) followed by taper
 
• Add prophylactic antibiotics for opportunistic infections
 
	
 
• Monitor participants for signs and symptoms of pneumonitis
 
• Evaluate participants with suspected pneumonitis with radiographic imaging and initiate corticosteroid treatment
 

	Recurrent Grade 2, Grade 3 or 4	Permanently discontinue		
Diarrhea/Colitis	Grade 2 or 3	Withhold	
 
• Administer corticosteroids (initial dose of 1 to 2 mg/kg prednisone or equivalent) followed by taper
 
	
 
• Monitor participants for signs and symptoms of enterocolitis (ie, diarrhea, abdominal pain, blood or mucus in stool with or without fever) and of bowel perforation (ie, peritoneal signs and ileus)
 
• Participants with ≥Grade 2 diarrhea suspecting colitis should consider GI consultation and performing endoscopy to rule out colitis
 
• Participants with diarrhea/colitis should be advised to drink liberal quantities of clear fluids. If sufficient oral fluid intake is not feasible, fluid and electrolytes should be
 

	Recurrent Grade 3 or Grade 4	Permanently discontinue		

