**Note: Non-irAE will be managed as appropriate, following clinical practice recommendations.**

a AST/ALT: >3.0 to 5.0 x ULN if baseline normal; >3.0 to 5.0 x baseline, if baseline abnormal; bilirubin:>1.5 to 3.0 x ULN if baseline normal; >1.5 to 3.0 x baseline if baseline abnormal

b AST/ALT: >5.0 to 20.0 x ULN, if baseline normal; >5.0 to 20.0 x baseline, if baseline abnormal; bilirubin:>3.0 to 10.0 x ULN if baseline normal; >3.0 to 10.0 x baseline if baseline abnormal

c AST/ALT: >20.0 x ULN, if baseline normal; >20.0 x baseline, if baseline abnormal; bilirubin: >10.0 x ULN if baseline normal; >10.0 x baseline if baseline abnormal

d The decision to withhold or permanently discontinue pembrolizumab is at the discretion of the investigator or treating physician. If control achieved or ≤ Grade 2, pembrolizumab may be resumed.

e Events that require discontinuation include, but are not limited to: encephalitis and other clinically important irAEs (e.g., vasculitis and sclerosing cholangitis).

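### For AST/ALT above 3.0 and up to 5.0 x ULN (normal baseline), Section 5.2 continues vorinostat at a lower dose while Section 5.2.2 requires a hold; bilirubin has the same conflict

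*Combined protocol and SAP*

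**What the plan says.** **Vorinostat table (Section 5.2, Non-hematological toxicities).**
- AST/ALT 2.5-5 x ULN: "First occurrence: 75 %: 300 mg qd Second occurrence: 50 %: 200 mg qd". No hold is stated.
- AST/ALT above 5 x ULN: "First occurrence: hold until ≤grade 2, resume at 75 %: 300 mg qd". A second occurrence leads to a further reduction, and a third takes the patient off study.
- Bilirubin 1.6-3.0 mg/dl: 300 mg, no hold stated. Above 3.0 mg/dl: "First occurrence: hold until ≤grade 2, 75 %: 300 mg qd".

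**Table 5.4 (Section 5.2.2).** Raised AST, ALT or bilirubin is a listed event. Pembrolizumab is withheld at grade 2 and permanently discontinued at grade 3 or 4. Footnote a sets grade 2 as "AST/ALT: >3.0 to 5.0 x ULN if baseline normal", and for bilirubin as above 1.5 and up to 3.0 x ULN. If baseline is abnormal, the same multiples apply to the baseline value.

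**Attribution and holding.** Three places address which drug is acted on:
- Section 5.2, opening: "The AE may be due to pembrolizumab or vorinostat alone in which case the respective agent should be reduced". The next sentence allows both drugs to be reduced if overlapping toxicity is suspected.
- Section 5.2.2, Attribution of Toxicity: "for adverse events listed in Table 5.4, both interventions must be held according to the criteria in Table 5.4". The same sentence expressly includes events attributed to vorinostat or tamoxifen alone.
- Section 5.2.2, Holding Study Interventions: "if the AE is considered immune-related, both interventions should be held according to recommended dose modifications".

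**Restart.** Under Restarting Study Interventions, if the toxicity does not resolve or the conditions for resuming are not met, "the participant must be discontinued from all study interventions".

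**The concern.** An Arm A patient with a normal baseline and AST at 4 x ULN falls under two instructions at once. The vorinostat table continues the drug at a reduced dose. The attribution paragraph with Table 5.4 holds it. The protocol does not say which takes precedence, and its three statements on attribution do not agree on whether the suspected cause matters.

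Two investigators could treat identical patients differently and both be following the text. The first consequence is for patient safety, because the disagreement concerns liver toxicity. The second is that vorinostat exposure could vary for reasons the protocol did not intend.

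**Working it through.** The protocol states no figure to reproduce. The check is to read each liver value through both sets of rules.

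**AST/ALT, normal baseline**

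| AST/ALT (x ULN) | Section 5.2 vorinostat table | Table 5.4, extended to both interventions by the attribution paragraph | Result |
|---|---|---|---|
| 2.8 | continue, reduced | below grade 2, no hold | no clash |
| 3.5 | continue, reduced | grade 2, withhold | direct clash |
| 4.5 | continue, reduced | grade 2, withhold | direct clash |
| 5.5 or 10 | hold, restart reduced at grade 2 or lower | grade 3, pembrolizumab permanently discontinued | both stop first; restart unclear |
| 25 | as above | grade 4, pembrolizumab permanently discontinued | as above |

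Share of the 2.5-5 row in direct conflict: (5.0 - 3.0) / (5.0 - 2.5) = 2.0 / 2.5 = 80%.

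**Bilirubin, normal baseline.** The protocol gives no ULN in mg/dl, so I assume U = 1.0 to 1.3 mg/dl. Grade 2 runs from above 1.5U to 3.0U, and 3.0U is at least 3.0 mg/dl throughout this range. The share of the 1.6-3.0 mg/dl row that is also grade 2 is [3.0 - max(1.6, 1.5U)] / 1.4.

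| U (mg/dl) | Grade 2 begins above (mg/dl) | Share of the row |
|---|---|---|
| 1.0 | 1.50 | (3.0 - 1.60) / 1.4 = 100% |
| 1.1 | 1.65 | (3.0 - 1.65) / 1.4 = 96% |
| 1.2 | 1.80 | (3.0 - 1.80) / 1.4 = 86% |
| 1.3 | 1.95 | (3.0 - 1.95) / 1.4 = 75% |

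The conflict is present at every assumed ULN; only its width changes.

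**Abnormal baseline.** Section 3.3.1 admits AST/ALT up to 5.0 x ULN with liver tumor. From a baseline of 4 x ULN, Table 5.4 grade 2 is above 3 x 4 = 12 and up to 5 x 4 = 20 x ULN. A value of 6 x ULN is then 6 / 4 = 1.5 times baseline, which is below grade 2, yet it exceeds 5 x ULN and triggers a vorinostat hold in Section 5.2. Here the rules diverge in the opposite direction, because only one of them adjusts for baseline.

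**Attribution.** Take a hepatic event attributed to vorinostat alone. The Section 5.2 opening reduces vorinostat. The attribution paragraph holds both interventions. The holding paragraph requires a hold only if the event is considered immune-related. These are three different answers. It is also unclear which drugs are meant by both interventions in a three-drug arm, although the attribution paragraph does name vorinostat.

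**The case against.** **The two tables divide by cause, not by laboratory value.** This is the strongest defence. Section 5.2.2 is headed as covering immune-related events, as is the first column of Table 5.4. Section 5.2.2 asks for evaluation to establish the cause. The holding paragraph is conditional on immune-relatedness, and a note to Table 5.4 leaves other events to clinical practice. The vorinostat table, for its part, applies to clinically relevant, drug-related abnormalities that are not due to progression. If this were all, the conflict would largely disappear. It remains because the attribution paragraph reaches events attributed to vorinostat alone, makes the hold mandatory, and gives as its reason that attribution is difficult. The scope wording elsewhere then contradicts that paragraph.

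**A tie-break already exists.** The most-stringent rule in Section 5.2 follows a sentence on febrile neutropenia and blood counts and is defined by size of dose reduction. Section 5.2.5 ranks organ systems. Neither ranks a hold against a reduction for one liver value.

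**Stronger readings that the documents do not support:**
- *Vorinostat must stop permanently above 5 x ULN, or conversely restarts automatically from any height.* The discontinuation column names pembrolizumab only, and extending it to vorinostat is inference. Section 5.2 also limits restart: if grade 3 or 4 liver toxicity persists after vorinostat is interrupted, both drugs stop; rechallenge goes to the study chair; a third AST/ALT occurrence above 5 x ULN ends participation.
- *A bilirubin above 3.0 mg/dl meets its hold and release conditions together.* With an assumed ULN of 1.2 mg/dl, values up to 3.6 mg/dl are still grade 2, so this would happen. With 1.0 it does not.
- *The pilot shows how often the conflict will arise.* The 2/34 (6%) reported in Sections 1.3.1.2 and 1.5 is grade 3-4 immune hepatitis, not the grade 2 band.
- *The comparison of Arm A with Arm B is biased.* Vorinostat is given only in Arm A, but efficacy is analysed by intention to treat (Section 8.3.1), and nothing in the documents allows an effect on response to be estimated.

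**Conclusion.** The text is wrong as written, within limits.

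- **Established:** with a normal baseline, AST/ALT above 3.0 and up to 5.0 x ULN carries two incompatible vorinostat instructions. Values of 2.5-3.0 x ULN do not.
- **Established, width dependent on the assumed ULN:** the same conflict covers about 75-100% of the 1.6-3.0 mg/dl bilirubin row for a ULN of 1.0-1.3 mg/dl. The scales differ: mg/dl in the vorinostat table, multiples of ULN in eligibility, multiples of ULN or baseline in Table 5.4.
- **Established:** the three statements on attribution do not agree.
- **Inference only:** above 5 x ULN both rules stop dosing at first. Reading the attribution and restarting paragraphs together, it is unclear whether vorinostat may restart under Section 5.2 once pembrolizumab has been permanently discontinued for a grade 3-4 hepatic event.
- **Not quantified:** how many patients would be affected, and any effect on the comparison of arms.

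This is a contradiction between passages. It says nothing about which clinical rule is right.

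**What to change.** Reconcile the opening of Section 5.2, its bilirubin and AST/ALT rows, the Attribution, Holding and Restarting paragraphs of Section 5.2.2, and the hepatic row and footnotes of Table 5.4. The amended text should:

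1. State which rule governs vorinostat when a liver value also meets Table 5.4, and which drugs are meant by both interventions in Arm A.
2. State whether attribution or immune-relatedness changes that, using one rule throughout.
3. State whether vorinostat may restart after pembrolizumab is permanently discontinued for a hepatic event.
4. Put the bilirubin and AST/ALT bands on the same ULN/baseline scale.

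The sponsor decides the clinical actions. The cost is table and text wording in an amendment, with the approvals that Section 9.4 requires. It adds no tests, visits or patients.
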